- v* Investigator will examine each participant's joints per the Haemophilia Joint Health Score (HJHS). At baseline, the Investigator will assess the presence of any target joints according to the International Society on Thrombosis and Haemostasis (ISTH) criteria.
- w* For bleeding episodes initially treated at the study sites, the Investigator will contact the caregiver approximately 72 hours from the time the BIVV001 injection was administered to treat the bleeding episode at the study site and record the caregiver's assessment of response to BIVV001 treatment on the eCRF using a 4-point bleeding response scale. For bleeding episodes that are treated at home, caregivers will record response to bleeding episodes in the ePD.
- x* Samples will be collected prior to any BIVV001 dosing and will be archived by the central laboratory (if required) for future research, eg, immunology assays, further coagulation assays, or clarification of any clinical or laboratory AE, etc. This is optional and participants/caregivers will sign an additional consent for this research.
- y* At the screening visit, caregivers will be shown and trained on the ePD device to ensure understanding of obligation to enter data during the trial. Devices will be given to caregivers at the baseline visit.
- z* Caregivers will record all bleeding episodes in the ePD beginning at Baseline. Assessment of response to bleeding episodes will be performed using a 4-point bleeding response scale. The caregiver should record response approximately 72 hours from the time the first BIVV001 injection was administered to treat the bleeding episode, unless treatment of the bleed was administered in the clinic. In that case, the investigator will report the caregiver's response to treatment via the eCRF.
- aa* The first 12 participants in each age cohort will undergo PK sampling after the first dose of BIVV001 (Baseline). Thereafter, PK sampling at Baseline will be optional. See PK sampling details in [Table 2](#).
- bb* Trough and peak samples are collected within 30 minutes prior to rFVIIIFc-VWF-XTEN dosing and 15 (\pm 3) minutes post-injection, respectively. This trough sample should be collected at the same time point as the trough inhibitor and ADA samples taken predose.

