
 To evaluate the efficacy of BIVV001 as a prophylaxis treatment To evaluate the efficacy of BIVV001 in the treatment of bleeding episodes To evaluate BIVV001 consumption for prevention and treatment of bleeding episodes To evaluate the effect of BIVV001 prophylaxis on joint health outcomes To evaluate the effect of BIVV001 prophylaxis on Quality of Life (QoL) outcomes To evaluate the efficacy of BIVV001 for perioperative management 	
 Annualized bleeding rate (ABR) (for treated, for untreated, for all bleeding episodes) and by type and location Percentage of participants who maintain FVIII activity levels over 1%, 3%, 5%, 10%, 15%, and 20% at Day 7 Number of injections and dose of BIVV001 to treat a bleeding episode Percentage of bleeding episodes treated with a single injection of BIVV001 Assessment of response to BIVV001 treatment of individual bleeding episodes based on the International Society on Thrombosis and Haemostasis (ISTH) 4-point response scale Physician's global assessment (PGA) of participant's response to BIVV001 treatment based on a 4-point response scale Total annualized BIVV001 consumption per participant Annualized joint bleeding rate (AJBR) Target joint resolution at Week 52, based on ISTH criteria Change from Baseline to Week 52 in total score and domain scores (eg, swelling and strength) assessed by the Hemophilia Joint Health Score (HJHS) Changes in Haemophilia Quality of Life Questionnaire for Children (Haemo-QoL) total score and physical health domain score from baseline to Week 52 (≥4 years old) and via parent proxy version (≥4 years old) Investigators' or Surgeons' assessment of participant's hemostatic response to BIVV001 treatment on the ISTH 4-point response for surgical procedures scale Number of injections and dose to maintain hemostasis during perioperative period for major surgery Total BIVV001 consumption during perioperative period for major surgery Number and type of blood component transfusions used during perioperative period for major surgery Estimated blood loss during perioperative period for major surgery

Objectives	Endpoints

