- Traumatic bleeding episodes: Bleeding episodes are classified as traumatic if the participant or caregiver records a bleeding episode when there is a known or believed reason for the bleed. For example, if a participant exercised strenuously and then had a bleeding episode in the absence of any obvious injury, the bleeding episode is still recorded as traumatic. Target joint bleeding episodes can be traumatic if a known action led to bleeding into the joint.

During the clinic visits and telephone calls with the participant's caregiver, the Investigator will review the bleeding episode data in the ePD. If the Investigator judges that the classification by the participant's caregiver was incorrect, the Investigator will document it in the participant's medical records with the rationale for the new classification, and in the eCRF, documenting the new classification of the bleeding episode according to the Investigator and whether or not the participant's caregiver agreed with this new classification.

Bleeding episodes will be reported for each participant during the treatment period, either in the ePD or the eCRF, as follows:

- Bleeding episodes and doses to treat bleeding episodes outside the clinic: Participant's caregiver completion and Investigator review of the participant's ePD are captured by the participant's caregiver using the ePD. The date and details of injection and bleeding episodes will be recorded by the participant's caregiver in the ePD within 7 days of the episode.
- Bleeding episodes in-clinic/hospital and doses to treat bleeds given at the clinic/hospital are captured by the Investigator in the eCRF.

- Electronic patient diary (ePD) Review and Training: Investigator or designee to review ongoing ePD data and perform participant retraining as necessary.
- Assessment of response to treatment of a bleeding episode, using 4-point bleeding response scale based on ISTH definitions:
 - Bleeding episodes that occur outside the clinic/hospital: assessment of response will be recorded in ePD for each bleeding episode.
 - Bleeding episodes treated in the clinic/hospital: assessment of response will be obtained from the participant by the Investigator and recorded in the eCRF.

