8.1.3 Assessment of clinical response to BIVV001 treatment for bleeding episodes

The ISTH 4-point assessment scale of treatment of acute bleeds will be used throughout the study for the assessment of response to treatment with BIVV001 for bleeding episodes (43) (Table 8). The assessment should be performed approximately 72 hours after the initial treatment for the bleeding episode.

Table 8 - ISTH assessment of treatment of acute bleeds

Excellent	Complete pain relief within 8 h and/or complete resolution of signs of bleeding after the initial injection and not requiring any further replacement therapy for relief of persistent symptoms and signs in the same joint within 72 h
Good	Significant pain relief and/or improvement in signs of bleeding within approximately 8 h after a single injection, but requiring more than one dose of replacement therapy within 72 h for complete resolution
Moderate	Modest pain relief and/or improvement in signs of bleeding within approximately 8 h after the initial injection and requiring more than one injection within 72 h but without complete resolution
None	No or minimal improvement, or condition worsens, within approximately 8 h after the initial injection

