The percentage of participants with resolution of at least 1 target joint and the percentage of total target joints that are resolved at 52 weeks will be summarized. A target joint is defined as a major joint (eg, hip, elbow, wrist, shoulder, knee or ankle) into which ≥ 3 spontaneous bleeding episodes occurred in a consecutive 6-month period and resolution is achieved when ≤ 2 bleeding episodes occur into that joint during 12 months of continuous exposure.

The consumption of BIVV001 will be annualized and summarized.

The number of injections and total dose of BIVV001 to treat a bleeding episode will be summarized on both a per-bleeding-episode and a per participant basis, where the per-participant basis will be determined as the average over all bleeding episodes for a given participant.

The participant's response to treatment of individual bleeding episodes will be summarized as the number and percentage of bleeding episodes with each response (excellent, good, moderate, or none).

The physician's global assessment of the participant's overall response to BIVV001 treatment will be summarized for each study visit and across all visits as the number and percentage classified as excellent, effective, partially effective, and ineffective.

For Haem-A-QoL, total score and physical health domain score will be summarized descriptively over time.

Surgical endpoints will be summarized descriptively for the surgical subgroup. Continuous endpoints will be summarized using the number of non-missing values (n), mean, SD, median, minimum, and maximum. Categorical endpoints will be summarized by counts and percentages.

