4.4.7 Assessment of response to BIVV001 treatment of bleeding episodes

Participants will provide an assessment of response to each injection of BIVV001 for treating a bleed using a 4-point scale of excellent, good, moderate, and none, based on ISTH standardized definitions in hemophilia (1). Response categories of excellent and good will be presented combined as well as individually.

The assessment of response will be summarized first on a per injection basis. The number and percentage of injections in each response category will be tabulated based on all injections; percentages will be based on the total number of injections for treating a bleed for which a response was provided.

As a supplemental analysis, the assessment of response will also be summarized on a per bleeding episode basis by presenting the number and percentage of first injections to treat a bleeding episode for which the response to the treatment was categorized as excellent, good, moderate, or no response. Percentages will be based on the number of bleeding episodes for which a response was provided for the first injection.

The participant's assessment of response during the efficacy period will be summarized by age cohort as well as overall for the FAS.

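### SAP 4.4.7 puts response per injection first and makes the per-episode summary supplemental, although the protocol endpoint is response per bleeding episode

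*SAP*

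**What the plan says.** The protocol treats the bleeding episode as the unit throughout.

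- Endpoint (Section 3, Table 4): "Assessment of response to BIVV001 treatment of individual bleeding episodes", on the ISTH 4-point scale. SAP Section 1.2, Table 2 lists the same endpoint.
- Timing (Section 8.1.3): "The assessment should be performed approximately 72 hours after the initial treatment for the bleeding episode". Footnote z to the Schedule of Activities (Section 1.3, Table 1) agrees: "The caregiver should record response approximately 72 hours from the time the first BIVV001 injection was administered to treat the bleeding episode".
- Collection for bleeds outside the clinic (Section 8.1.2): "assessment of response will be recorded in ePD for each bleeding episode".
- Analysis (Section 9.4.3): the response "will be summarized as the number and percentage of bleeding episodes with each response (excellent, good, moderate, or none").

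SAP 4.4.7 changes the unit. On collection it says: "Participants will provide an assessment of response to each injection of BIVV001 for treating a bleed". On analysis it says: "The assessment of response will be summarized first on a per injection basis". The percentages use as denominator the bleed-treating injections that have a rating. The per-episode summary follows as a supplemental analysis, using the rating of the first injection and counting episodes with such a rating. The section gives no reason for the change.

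**The concern.** The SAP reverses the order of the two summaries relative to the protocol. It does not use the term main analysis, but placing one summary first and calling the other supplemental sets a hierarchy, and it is not the protocol's. A reader of the results would not know which percentage is the result for the endpoint.

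Two further problems go beyond table order. First, the SAP assumes a rating for every injection, and no protocol text asks for one. Second, the ISTH grades in Protocol Table 8 describe the course of the whole episode. Excellent requires that no further replacement therapy was needed within 72 hours. Good is a bleed "requiring more than one dose of replacement therapy within 72 h for complete resolution". Moderate also presupposes more than one injection. Grading a follow-up injection by itself on this scale has no clear meaning.

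**Working it through.** The plan states no figure for this endpoint, so there is nothing to reproduce. The check is a comparison of texts, followed by arithmetic on an assumed set of bleeds to see whether the unit matters.

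**Texts compared**

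| Item | Protocol | SAP 4.4.7 |
|---|---|---|
| What is rated | Each episode (8.1.2) | Each injection |
| When | About 72 h after initial treatment (8.1.3; Table 1, footnote z) | Not stated |
| Denominator of the stated or first-listed summary | Episodes (9.4.3) | Rated injections |
| Per-episode summary | The planned summary | Supplemental |

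**Inputs (assumed, not trial data).** There are E = 100 treated episodes, of which m need k injections each. Every single-injection episode is rated excellent or good. Every multi-injection episode is rated moderate or none at the first injection.

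**Formulas**

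- Injections: I = (E − m) + m·k
- Per-episode rate: (E − m)/E
- Per-injection rate, follow-up injections also moderate or none: (E − m)/I
- Per-injection rate, follow-up injections excellent or good: [(E − m) + m(k − 1)]/I
- Per-injection rate, only first injections rated: (E − m)/E

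**Example, m = 20 and k = 2.** I = 80 + 40 = 120.

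- Per episode: 80/100 = 80.0%
- Per injection, low end: 80/120 = 66.7%
- Per injection, high end: (80 + 20)/120 = 83.3%
- Per injection, only first injections rated: 80/100 = 80.0%

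**Other assumed mixes**

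| m of 100 | k | Per episode | Per injection, all injections rated | Only first injections rated |
|---|---|---|---|---|
| 5 | 2 | 95.0% | 90.5% to 95.2% | 95.0% |
| 10 | 2 | 90.0% | 81.8% to 90.9% | 90.0% |
| 10 | 3 | 90.0% | 75.0% to 91.7% | 90.0% |
| 20 | 3 | 80.0% | 57.1% to 85.7% | 80.0% |
| 30 | 2 | 70.0% | 53.8% to 76.9% | 70.0% |

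**Effect of the Good grade.** The assumption that every multi-injection bleed is moderate or none is severe, because Good covers bleeds that resolved after more than one dose. If all 20 two-injection bleeds, and their follow-up injections, were rated good, the combined excellent-or-good rate would be 100/100 per episode and 120/120 per injection, so 100% on both. The excellent category alone would still differ: 80/100 = 80.0% against 80/120 = 66.7%.

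**The case against.** The strongest case on the other side has four parts.

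1. **The two tables may be identical.** The SAP denominator contains only injections that have a rating. With one rating per episode, attached to the first injection, follow-up injections drop out. This stands, and it limits the point. A reader might infer that hard-to-treat bleeds will be counted several times, so that, for example, 90.0% becomes 75.0% (the row with 10 of 100 bleeds needing three injections). The documents do not support that as a prediction. It needs poor ratings on the follow-up injections, either collected separately or copied from the episode. The SAP has no copying rule. It also needs no three-injection bleed to be rated good.

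2. **Collection is less certain than the clearest passages suggest.** Footnote w to Table 1 and footnotes k and m to Table 3 time the rating from the injection without saying the first. The diary prompts in Protocol 4.1 and 8.1.1 list response to treatment next to the reason for dosing. The ePD specification is not in the documents. If the diary does take a response with each treatment entry, the SAP sentence describes the data correctly. This stands in part: it makes any correction of that sentence conditional. It does not change the endpoint's unit.

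3. **Nothing in the protocol's analysis is lost.** The per-episode table is still planned, anchored to the first injection as the protocol requires. Injections per bleed and single-injection bleeds are reported under SAP 4.4.5 and 4.4.6. This is correct: the per-episode result is demoted, not dropped. Planning both tables still leaves open which one answers the endpoint.

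4. **The stakes are low.** The endpoint is one of many secondary ones, no hypothesis is tested (Protocol 9.1), and multiplicity is not adjusted (SAP 4.6). Protocol 4.3 expects most bleeds to need one dose. This also stands.

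**Conclusion.** The conflict is real and its consequence is limited. SAP 4.4.7 departs, without a stated reason, from the unit set by the protocol and kept in the SAP's own Table 2, and it assumes ratings that the protocol does not ask for.

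The size depends on the data collected. If only the first injection carries a rating, the difference is zero. If follow-up injections carry ratings too, the illustration with 20 of 100 bleeds needing two injections runs from 13.3 percentage points below the per-episode rate (80.0 − 66.7) to 3.3 points above it (83.3 − 80.0). The direction is not fixed. Those figures rest on an assumed share of multi-injection bleeds and on none of those bleeds being rated excellent or good at the first injection. They show sensitivity and do not forecast the trial result.

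It would go too far to conclude that the reported response rate will be wrong or biased in a known direction. No test or decision rule depends on it.

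**What to change.** In SAP 4.4.7:

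- Make the per-episode summary the main analysis, with rated episodes as the denominator. Report the number of episodes without a rating.
- Keep the per-injection table as supplemental only if ratings are actually collected for follow-up injections. In that case, state how a follow-up injection is graded on the ISTH scale. Otherwise drop the table.
- Check the sentence saying that each injection is rated against Protocol 8.1.2, 8.1.3 and Table 1 footnote z, and against the ePD specification. Then align the wording with what the diary records.

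The cost is a wording change before database lock. Both tables are already planned, and no new data are needed. The count of unrated episodes is a small addition to the per-episode table.

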4.4.8 Physician's global assessment of participant's response to BIVV001 treatment

The physician's global assessment of the participant's response to BIVV001 treatment will be summarized by age cohort and overall for each study visit as the number and percentage of participants classified as excellent, effective, partially effective, and ineffective. Percentages will be based on number of participants for whom an assessment was provided at the respective visit.

Statistical Analysis Plan
BIVV001-EFC16295

This table will also include a cumulative tabulation across all scheduled study visits; participants can be included in this tabulation once for each visit. Percentages for this collection of responses throughout the study will be based on the total number of assessments across all visits.

4.4.9 Annualized BIVV001 consumption

The consumption of BIVV001 will be annualized and summarized by age cohort and overall for the FAS. The total annualized BIVV001 consumption (IU/kg) will be calculated for each participant using the following formula:

Annualized consumption =
$$\frac{\text{Total IU/kg of BIVV001 during the efficacy period}}{\text{Total number of days during the efficacy period}} \times 365.25$$

The total amount of BIVV001 received will be the sum of the nominal IU/kg administered for each injection based on the units of BIVV001 as recorded from the participant's ePD and eCRF and the participant's most recent weight.

Total annualized BIVV001 consumption will be determined for the efficacy period, ie, excluding the PK assessments and surgery/rehabilitation periods (major or minor).

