4.1.1.1 Treatment period

The treatment period is defined as the actual treatment that the participant follows.

The start date and time of the treatment period is defined as the date and time of the first dose of study drug (or, if the time is not available, at 00:01 on the day of the first dose). The end date and time of the treatment period is defined as 23:59 on the day of the last dose of study drug.

The duration of treatment period is the time period from the start of the treatment period to the end of that treatment period. The total duration will be calculated in minutes and converted to days as the number of minutes divided by 1440.

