4.1.1.2 Efficacy period

The efficacy period will be used for the evaluation of bleeding and consumption endpoints. For a participant to have an evaluable efficacy period over the duration of study, he/she must have at least 2 prophylactic dose of study drugs. The efficacy period is defined as the treatment period interrupted for PK periods, surgical/rehabilitation periods (major and minor) and large injection intervals as described below.

Adjustments Due to PK sampling period(s)

For participants undergoing PK sampling after their first dose of BIVV001, the efficacy period starts with the date and time of the first prophylactic dose following the completed PK sampling period (168 hours), and ends with the end of the treatment period as defined in Section 4.1.1.1. That is, if the initial PK sampling period is incomplete due to an aborted collection of blood samples following the PK injection (eg, because of a bleeding episode that required treatment), then the efficacy period will begin following a subsequent fully executed PK sampling period.

Adjustments Due to Surgical/Rehabilitation Periods

For analysis purposes, the efficacy period will be adjusted for all surgical/rehabilitation periods (major and minor). The start and end of the efficacy period are adjusted as follows:

- For all participants, the efficacy period continues up to 1 minute before the start of a surgical/rehabilitation period.
- For participants on a prophylactic regimen following the end of a surgical/rehabilitation period, the efficacy period for the prophylactic regimen re-starts at the first prophylactic dose following the end of the surgical/rehabilitation period.

Statistical Analysis Plan BIVV001-EFC16295 23-Aug-2021 Version number: 1

Bleeding episodes that occur during the surgical/rehabilitation period will be attributed to the surgical/rehabilitation period and hence not counted towards the ABR.

Adjustments Due to Large Injection Intervals

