For analysis purposes, the efficacy period will also be adjusted to account for large intervals between injections resulting from missing data. A large interval is defined as >28 days between any 2 adjacent BIVV001 injections within a prophylactic treatment regimen, and any such intervals will be removed from the efficacy period. The efficacy period prior to each such interval will end at the time of the last injection prior to the interval and restart at the time of the next prophylaxis injection. The efficacy period will be adjusted for each identified interval that is not within a surgical/rehabilitation period.

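### Annualized consumption counts the final dose in full but less than one of the seven days it covers, so it is overstated when the efficacy period ends at a last dose: about 2% for completers, more for early leavers.

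*SAP*

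**What the plan says.** The numerator is set in SAP 4.4.9: "The total amount of BIVV001 received will be the sum of the nominal IU/kg administered for each injection". No rule there or elsewhere in the SAP removes the last dose. The denominator in the same section is "Total number of days during the efficacy period".

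The length of that period follows from two definitions. SAP 4.1.1.2: "The efficacy period is defined as the treatment period interrupted for PK periods, surgical/rehabilitation periods (major and minor) and large injection intervals as described below". SAP 4.1.1.1: "The end date and time of the treatment period is defined as 23:59 on the day of the last dose of study drug". For the PK subgroup, SAP 4.1.1.2 repeats that the efficacy period "ends with the end of the treatment period as defined in Section 4.1.1.1".

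SAP 4.1.1.2 adds three rules that matter here:

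- **Minimum data.** To have an evaluable period, "he/she must have at least 2 prophylactic dose of study drugs".
- **Large intervals.** When a gap of more than 28 days is removed, the preceding period "will end at the time of the last injection prior to the interval and restart at the time of the next prophylaxis injection".
- **Surgery.** The period runs until one minute before the surgical/rehabilitation period starts.

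**The concern.** A weekly dose is meant to cover seven days. If the numerator takes the final dose whole while the clock stops on the day it is given, then n doses are divided by roughly n−1 weeks. The excess is about 1/(n−1), so it is small after a year and large after a few weeks. It always points upward, and a larger sample does not average it out.

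Total annualized consumption per participant is a named secondary endpoint and the only one listed for its objective (Protocol section 3, Table 4). Each participant's ratio has equal weight in the mean, so a few short periods can move it. Short periods can arise without dropout, because Protocol 4.4 recalls all ongoing participants once the study milestones are met. SAP 4.4.1.3 gives ABR a sensitivity analysis limited to efficacy periods of at least 26 weeks; consumption has none.

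**Working it through.** The documents give no consumption figure to reproduce, so the SAP formula is applied directly.

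**Inputs from the documents.** 50 IU/kg every 7 days (Protocol 6.1.2); 52 weeks of treatment, with an in-clinic dose marked at the Week 52 visit (Protocol Table 1), hence up to 53 doses over 364 days; factor 365.25 (SAP 4.4.9).

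**Assumptions.** Exact doses and intervals, no bleed doses, no surgery. f is the part of the last dosing day counted up to 23:59: 0.58 day for a 10:00 dose, and between 0 and 1 day for any clock time.

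**Formulas.** For n doses, SAP value = 365.25 × 50n / (7(n−1) + f). Regimen rate = 365.25 × 50 / 7 = 2608.9 IU/kg/year.

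| Last dose | n | SAP value, f = 0.58 | Excess | Range, f = 1 to f = 0 |
|---|---|---|---|---|
| Week 52 | 53 | 2650/364.58 × 365.25 = 2654.9 | +1.8% | 1.6 to 1.9% |
| Week 26 | 27 | 1350/182.58 × 365.25 = 2700.7 | +3.5% | 3.3 to 3.8% |
| Week 13 | 14 | 700/91.58 × 365.25 = 2791.8 | +7.0% | 6.5 to 7.7% |
| Week 4 | 5 | 250/28.58 × 365.25 = 3195.0 | +22.5% | 20.7 to 25.0% |
| Week 1 (two doses) | 2 | 100/7.58 × 365.25 = 4818.6 | +84.7% | 75 to 100% |

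The Week 52 excess is 2654.9 − 2608.9 = 46 IU/kg/year.

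**PK subgroup.** The period starts at the second dose, so n falls by one: +1.8% at Week 52 and +29.7% at Week 4.

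**Large interval.** Take a completer with one 35-day gap. Four doses are missed, leaving 49. The gap replaces five of the 52 intervals, leaving 47 × 7 + 0.58 = 329.58 days. The result is 2450/329.58 × 365.25 = 2715.2, or +4.1%.

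**Segment ending at surgery.** With 26 weekly doses and the surgical period starting d days after the last, the denominator is 25 × 7 + d. The error is 0% at d = 7, +3.4% at d = 1 and −1.1% at d = 9. It depends on when surgery falls and can take either sign.

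**Cohort mean, illustrative only.** Among 65 participants, the rest completing:

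- 5 leaving at Week 4: (60 × 2654.9 + 5 × 3195.0)/65 = 2696.4, or +3.4%.
- 15 leaving at Week 26: (50 × 2654.9 + 15 × 2700.7)/65, about 2665, or +2.2%.

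**The case against.** The strongest reply is that IU used divided by days in the period is a literal observed rate. The protocol promises only an annualized summary, and the comparison with 2608.9 is a convention the documents never adopt. For most participants the difference is about 2%. The numerator is in nominal IU although actual potency may be 80% to 125% of nominal (Protocol 6.1.6.1). The large percentages describe single hypothetical participants, and the documents give no dropout timing. The median barely moves, and all analyses are descriptive (Protocol 9.1).

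Most of that stands as to weight. It does not remove the fault: a rate whose expected value depends on length of follow-up, under one unchanged regimen, is not a usable annual figure. Potency variation is a different kind of error and does not offset this one.

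A reader might infer more than the documents support:

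- **That none of the last dose's days are counted.** The rest of the dosing day is. Only before a removed large interval is the credit zero.
- **That every participant is affected.** Those with fewer than two prophylactic doses have no evaluable period. A segment ending at surgery keeps the days elapsed since its last dose.
- **That ABR is inflated too, since it shares the denominator.** This mechanism does not carry over. ABR counts bleeds within the same window as the days, and no week of drug cover is cut off from its count.

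**Conclusion.** The point holds in limited form. Where the efficacy period ends at a last dose, the SAP 4.4.9 formula overstates annualized consumption, and a removed large interval adds to the excess. Under the stated assumptions this is about 2% for completers, under 4% from Week 26, 7.0% at Week 13, and more than 20% only for exits around Week 4 or earlier. The two-dose figure of about 85% is the extreme that the eligibility rule allows, not an expected result. The effect on a cohort mean depends on unknown dropout timing; the two illustrations give +2.2% and +3.4%. No test, threshold or sample size is affected. The correction is worth making because the error is systematic, sits in a named secondary endpoint and is cheap to remove.

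**What to change.** Add a rule to SAP 4.4.9, for consumption only, leaving the ABR period unchanged. For each segment that ends at a last dose or at a large interval, but not at surgery, do one of the following:

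1. Leave the final prophylactic dose out of the numerator and stop the consumption denominator at the time of that dose.
2. Keep the dose and run the denominator for one dosing interval from its time, instead of ending at 23:59. Use the participant's own interval if it was shortened, as Protocol 6.1.2 allows in the younger cohort.

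Doses given to treat bleeds stay in the numerator. The rule should say what happens when the last dose of study drug is a bleed-treatment dose given after the final prophylactic one.

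Under exact weekly dosing, both options return 2608.9 at every follow-up length. In the gap example, option 1 gives 2350/329 × 365.25 and option 2 gives 2450/343 × 365.25, both 2608.9.

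Two shortcuts overcorrect. With two doses, dropping the last dose but keeping the 23:59 end gives 50/7.58 × 365.25 = 2409 (−7.7%). Adding seven days after 23:59 gives 100/14.58 × 365.25 = 2505 (−4.0%). Applying either option to a segment that ends at surgery would also be wrong, since that dose already has its elapsed days.

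The cost is a separate denominator for consumption, to be defined and programmed, and a slightly lower reported value. No new data are needed, and treatment and conduct do not change.
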